1 INTRODUCTION

Monitoring and detecting fluid changes in patients can be complicated. Physiological responses associated with hemorrhagic events are often delayed because of compensation mechanisms that act to sustain blood pressure and protect tissue perfusion. The ability to continuously and non-invasively detect changes in central blood volume and blood loss will permit appropriate hemodynamic management during events at high risk for acute blood loss such as surgery, trauma, post-operative care and other therapeutic procedures. Through early detection and improved hemodynamic monitoring, optimization of fluid balance, anesthesia titration, and augmenting other acute care management requirements, a clinician should be able to improve overall patient stability, minimize complications, diminish surgical trauma and reduce recovery time.

Current methods for acutely monitoring blood volume and blood loss include monitoring of vital signs (such as heart rate, blood pressure respirations, and oxygen saturation), invasive central venous (right heart central venous pressure measurement and swan ganz pulmonary capillary wedge pressure measurements), and arterial catheters designed to monitor hemodynamic status centrally. Vital sign monitoring may not indicate small amounts of acute blood loss and arterial and venous cannulations can create insertion complications such as perforations in the vasculature, pneumothorax, arrhythmias, thrombosis and infection. While invasive central monitoring may provide extremely accurate information, changes may not be good indicators of early central hypovolemia or with smaller blood volume reductions¹⁻².

The Zynex Monitoring Solutions fluid volume monitor, Model 1500 (CM-1500), uses a relative patient standard approach by non-invasively and simultaneously monitoring five (5) physiological parameters, including bioelectrical impedance, electrocardiogram (ECG) amplitude, photoplethysmogram (PPG) amplitude, heart rate, and skin temperature

When the monitoring session starts, each patient starts with a Relative Index of 100, signifying the collection of parameters near their original baseline value(s). The Relative Index value acts as a combinational score for all the parameters indicative of relative fluid change.

Hemodialysis is a medical procedure performed to remove fluid and waste products from the blood and to correct electrolyte imbalances. Patients with chronic kidney failure often need to undergo hemodialysis multiple times each week to prevent fluid overload. The environment in which hemodialysis is performed is well-defined, and the amount of fluid volume removed during each session is calculated and recorded. Therefore, examining changes in the RI in hemodialysis procedures will provide valuable insights into the performance of the RI in comparison to the individual parameters that make up the index, as well as the observed changes that may occur in a patient's physical status during a hemodialysis session.

SPONSOR: ZMS

PROTOCOL: ZMS-1500-2021-Dialysis

1.1 CLINICAL RATIONALE

The proposed clinical study is designed characterize the changes in the Zynex non-invasive monitoring device (CM-1500) Relative Index to track fluid volume changes in subjects consented to undergo a hemodialysis procedure. An initial feasibility was conducted (n=12 subjects) to confirm that the CM-1500 can be used to track acute blood loss in healthy individuals donating 500mL of blood,

Additional research is required to assess Relative Index changes when larger fluid volumes are observed and to determine how the individual parameters impact the overall device performance in a hemodialysis setting.

2 INVESTIGATIONAL PLAN

2.1 OBJECTIVES

The primary objective of the study is to characterize changes in the CM-1500 Relative Index during a hemodialysis procedure.

The secondary objective of the study is to characterize the intersubject and intrasubject variability in Relative Index changes across multiple hemodialysis sessions.

2.2 STUDY DURATION

Enrollment in the study is expected to take up to 3 months, and data analysis may take up to an additional 2 months to complete. Each individual subject's study participation is estimated to last approximately 1-2 weeks but may continue for up to 30 days. If the subject has not completed three (3) monitoring sessions within 30 days, participation will be considered complete, and the subject will be withdrawn from the study.

2.3 STUDY DESIGN

The study is a prospective, single-arm, non-randomized, non-blinded, non-controlled, non-significant risk, single center study enrolling subjects consented to undergo a hemodialysis session as a part of their standard prescribed treatment plan. Subjects will consent to undergo non-invasive monitoring with the CM-1500 during three (3) separate hemodialysis sessions. Attempts will be made to have the monitoring sessions sequentially performed with their subsequently planned hemodialysis sessions. Up to 20 subjects will be consented and enrolled to ensure 15 subjects complete the study with the required number of monitoring sessions.

3 STUDY DEVICE

3.1 DEVICE DESCRIPTION

The CM-1500 is a U.S. Food and Drug Administration (FDA) cleared non-invasive monitoring device that simultaneously monitors five (5) parameters of a patient's body. Parameters include bioelectrical impedance, heart rate, ECG amplitude, PPG amplitude, and skin temperature. A combination of these parameters is represented by a single number known as the Relative Index value.

The Relative Index is a unique functionality of the Zynex CM-1500.

CONFIDENTIAL Page 9 of 24

SPONSOR: ZMS

PROTOCOL: ZMS-1500-2021-Dialysis

3.1.1 DEVICE DESIGN AND COMPONENTS

The CM-1500 is an all-inclusive device that includes the following components: display monitor (1), power supply (1), trunk cable (1), wrist cuff with attached PPG finger glove (1), wrist strap (1), and electrode array set (2). The wrist cuff with attached PPG finger glove may be cleaned and reused. The wrist strap is single-subject use. The electrode array sets are single-use, single-subject.

3.2 PRINCIPLES OF OPERATION

The CM-1500 measures bioelectrical impedance (ohms), heart rate (BPM), ECG amplitude, PPG amplitude, and skin temperature (°C or °F). As parameters change, towards indications of fluid change/imbalance, the Relative Index, which acts as a combinational score will compound these changes into a singular value to signify overall fluid changes/imbalances within the patient's body. When the monitoring session starts, every patient will start with a Relative Index of 100, signifying the combination of physiological parameters is near or at their original baseline values for all five monitored parameters. All parameters are continuously measured and tracked during a monitoring

3.3 INDICATIONS FOR USE

Per the device's FDA clearance, the CM-1500 is indicated for monitoring bioelectrical impedance, heart rate, ECG amplitude, and PPG amplitude and their relative changes, indicative of relative changes in fluid volume in adult patients.

3.4 INTENDED USE

session.

Per the device's FDA clearance, the CM-1500 is intended to be used in professional medical environments, i.e., hospitals, clinics, and research institutions. The CM-1500 is a standalone device intended for desktop use, where device operation is to be performed as uninterrupted patient monitoring. The CM-1500 shall only be used by a qualified device operator. The operator shall have knowledge of the system and data interpretation obtained via medical education, system documentation, and specific courses. The device does not report any diagnosis but provides numerical values; it is ultimately the physician's responsibility to make proper diagnosis and judgments based on these values.

4 SUBJECT POPULATION AND SELECTION

4.1 POPULATION AND ANTICIPATED NUMBER OF SUBJECTS

Up to 20 adult subjects who meet the inclusion and exclusion criteria will be consecutively enrolled in the study. Subjects who enroll in the study but withdraw before using the device will not be included in the total number of subjects and will be replaced.

4.2 SUBJECT INCLUSION CRITERIA

- I.1 Ability to provide written informed consent
- 1.2 Ability and willingness to comply with the study procedures and duration requirements, including connection of the device to the left wrist/hand and maintaining relatively motionless during the session

CONFIDENTIAL Page 10 of 24

SPONSOR: ZMS

PROTOCOL: ZMS-1500-2021-Dialysis

- I.3 18 years of age or older
- 1.4 Planned to undergo a minimum of three (3) hemodialysis sessions within the two (2) weeks following enrollment.

4.3 SUBJECT EXCLUSION CRITERIA

- E.1 Females who are pregnant or breastfeeding
- E.2 Undergone an amputation of the left upper extremity
- E.3 Subjects with left arm hemodialysis access only
- E.4 Diagnosed with dextrocardia
- E.5 Subjects who have a pacemaker
- E.6 Subjects who have any other underlying condition that would inhibit completion of participation in the study, per Investigator opinion

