5.3 STUDY PROCEDURE

The study procedure will consist of connecting the CM-1500 to the study subject on their left arm/wrist and starting a monitoring session at least 5 minutes prior to starting the scheduled hemodialysis procedure, wearing the monitor during the hemodialysis session, and continuing to wear the monitor for 10 minutes after the procedure is complete. The Investigator's standard post-treatment hemodialysis record will be collected containing the prescription information, machine set-up, vitals, pre- and post-treatment data collection and assessment, medications administered, and intradialytics.

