5.3.2 PREPARING THE SUBJECT FOR DEVICE OPERATION

After the device is prepared for operation, the Investigator or qualified designated study personnel will prepare the subject for device operation by referencing the Instructions for Use (IFU) manual and following the steps outlined below. The subject will be placed in a supine or sitting position after the device is prepared for operation and maintain this position through observation.

- S9. Clean the subject's skin on his or her left wrist.
- S10. Take the small white connector/electrode array and remove the transparent plastic film attached to the electrodes to expose the adhesive. Place the small white connector/electrode array on the dorsal (top) of the subject's left wrist. The white connector shall be pointed medially (inward) towards the subject's body.
- S11. Take the large blue connector/electrode array and remove the transparent plastic film attached to the electrode to expose the adhesive. Place the large blue connector/electrode array on the left side of the neck's base and down across the front of the shoulder (above the clavicle). The blue connector shall point away from the neck, extending toward the direction of the left shoulder.
- S12. Place the wrist cuff on the subject's left wrist (above or over the top of the white electrode array), with the trunk cable connection pointing up the arm, and secure the wrist strap around the left wrist. The cuff should be snug with no gap between the wrist cuff and skin. The wrist cuff should not be able to slide or rotate on the wrist nor should it be too tight or restricting of blood flow.
- S13. Place the PPG finger glove on the subject's left digitus II manus (Index) fingertip. The white cable/top side of the finger glove should be on the dorsal (top) side of the finger. The fingertip shall be touching the end of the inside of the glove. Fingernails will often protrude through the end of the finger glove, which is normal.
- S14. Examine the trunk cable to ensure that it is connected securely to the CM-1500 display monitor and the wrist cuff.

CONFIDENTIAL Page 13 of 24

Z NEX

CLINICAL PROTOCOL

SPONSOR: ZMS

PROTOCOL: ZMS-1500-2021-Dialysis

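### As worded, E.3 allows a subject to be dialysed through an access on the monitored left side, and access side is neither a named data item nor a model term

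*Combined protocol and SAP*

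**What the plan says.** **Eligibility.** Exclusion E.3 (section 4.3) reads "Subjects with left arm hemodialysis access only". It is the only criterion that names vascular access. E.6 is a discretionary exclusion: "Subjects who have any other underlying condition that would inhibit completion of participation in the study, per Investigator opinion".

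**Sensor side.** Inclusion I.2 (section 4.2) requires willingness to comply, "including connection of the device to the left wrist/hand". Section 5.3 describes "connecting the CM-1500 to the study subject on their left arm/wrist". In section 5.3.2 the small array goes on the left wrist (step S9: "Clean the subject's skin on his or her left wrist"). The wrist cuff goes over or above it (S12: "The cuff should be snug with no gap between the wrist cuff and skin"), and the PPG glove goes on the left index finger (S13). The large blue array goes on the left "side of the neck's base and down across the front of the shoulder (above the clavicle") (S11). No section offers the right side.

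**Index and analysis.** Section 3.2 starts the Relative Index at 100 in each monitoring session. Section 5.3 starts monitoring at least 5 minutes before dialysis. Section 9.5 compares values during dialysis with that baseline, then fits a variance-component model with two random terms, subject and session.

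**Data collected.** Section 5.2 lists age, sex, smoking, some medication information and a broad medical history. Section 5.3 adds the site's dialysis record, whose listed contents include machine set-up and assessments before and after treatment. Section 5.4 adds the date of the last procedure and the number of unmonitored sessions in between. Access type and side are not named in any of these.

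**The concern.** E.3 suggests that the sponsor sees a conflict between left-arm access and left-sided sensors. The word only limits the exclusion to subjects with no alternative access. The conflict arises, however, from which access is used while the device is running, and the protocol does not control that.

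Both objectives in section 2.1 are at stake: the change in the index during dialysis, and its variability between and within subjects. Impedance, PPG amplitude and skin temperature contribute to the index (section 1), and the sensors are all on the left side. If blood is drawn and returned on that side, part of the recorded change may be local rather than a response to fluid removal. A mix of access sides across subjects would then add to the between-subject component. A change of side between one subject's sessions would add to the within-subject component.

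**Working it through.** There is no stated figure to reproduce. Section 9.1 calls the sample size empirical and gives no effect size or SD. The check sets the eligibility wording against the sensor placement.

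**1. E.3 by access situation**

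| Access | Excluded by E.3? | Dialysed on the monitored side? |
|---|---|---|
| Left arm, no other | Yes | Not enrolled |
| Left arm plus another, left arm used | No | Yes |
| Left arm plus another, other one used | No | Depends on the other site; an unused access remains on the monitored limb |
| Left neck catheter, no left-arm access | No | Yes, in the region of the blue array |
| Left chest catheter, no left-arm access | No | Same side; overlap with an array above the clavicle is not shown |
| Right arm, no other | No | No |

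The second and fourth rows are the gap.

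**2. Other filters.** E.6 and I.2 concern completing and complying. Withdrawal criteria W.2 and W.4 (section 4.4) concern compliance and the subject's interest. None concerns signal validity, and a subject in row two can comply and complete.

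**3. Baseline.** The index is set to 100 before dialysis starts. An effect present both before and during dialysis may be absorbed. An effect that starts with flow through a left-sided access begins after the baseline, in the same period as the change being measured, so it would not be absorbed.

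**4. Change over time.** Figure 1 places the eligibility check at enrollment. Participation may run up to 30 days (section 2.2). No later step asks about access.

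**5. Traceability.** Access side is not a named field (sections 5.2, 5.3, 5.4) and not a model term (section 9.5). Any effect would fall into the subject or the session/residual variance without a label.

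**6. What a shift would do.** Let d be an unknown shift, in index points, in the index change of an affected session. Assume a balanced set of 15 completers × 3 sessions = 45 values (sections 2.3 and 5.4), one index-change value per session, and a shift unrelated to the subject's own level.

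- One subject affected in all three sessions:
  - The mean moves by 3d/45 = d/15 = 0.067d.
  - The expected variance among subject means rises by d² × k(n − k)/[n(n − 1)]. With k = 1 and n = 15 this is d² × 14/(15 × 14) = d²/15. The residual is unchanged.
- One subject affected in one session:
  - The mean moves by d/45 = 0.022d.
  - The residual sum of squares rises in expectation by d² × (14/15) × (2/3) = 0.622d². On (15 − 1)(3 − 1) = 28 degrees of freedom, the residual mean square rises by 0.622d²/28 = d²/45.
- Section 9.2 analyses all eligible device users. If 20 subjects used the device and were weighted equally, one subject's share of the mean would be 1/20 = 5%.

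The variance terms grow with d², so a subject's influence on them is not a fixed share. The documents give neither d nor the number of affected subjects, which could be anywhere from none to all.

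**The case against.** The strongest reply is that only has a sensible purpose: to admit subjects who can be dialysed elsewhere. That is the likely intent and would be sound, but no section says that the other access must be used while the device is on.

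Several further points stand.

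- The index is rebased at each session, so a stable effect of an unused or maturing left-arm access may largely cancel.
- A left neck catheter that physically prevented placement of the blue array would make the procedure impossible, which W.2 would cover.
- The dialysis record collected at every session may show the access used, although the plan does not name it.
- This is a pilot without hypothesis tests, so no decision error rate is at risk.

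A reader might infer more than the documents support:

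- *That the index does reflect the access.* No section gives data on this; it is plausible, not shown.
- *That the sensors lie on the access.* A left-arm access need not be at the wrist or finger, and the blue array is above the clavicle, so overlap with a chest catheter is not established.
- *That the snug cuff is a hazard to an access limb.* Section 7.1 does not list it, but step S12 also warns against tightness that would restrict flow, and the Instructions for Use are not part of these documents.
- *That every left-sided access should be excluded.* Access in use and access not in use differ here, and a wider exclusion is a recruitment trade-off that the documents do not settle.

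**Conclusion.** The point holds in this form. E.3 does not prevent dialysis through an access on the monitored side, and the plan has no named item or model term by which such sessions could be recognised. An effect that starts with dialysis may therefore enter the primary description and the variance components.

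Its size cannot be derived. Per affected subject it is d/15 on a 15-subject mean and d²/15 on the between-subject variance; for a single affected session it is d²/45 on the residual mean square. All three rest on the balanced layout and the assumptions stated with the calculation, with d unknown. If no enrolled subject is dialysed on the left, this effect is absent.

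The change should be made because it is cheap and because section 9.1 says the results will help decide whether a powered study can be defined.

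**What to change.** 1. Reword E.3 so that eligibility depends on the access to be used in the monitored sessions not being in the left arm or at the blue-array site.
2. Confirm this at each of the three sessions, not only at enrollment.
3. Add one CRF line per session: type and side of the access used, and any other left-sided access present.
4. If access moves to the left, extend the section 5.4 provision for the next available session to this case where possible. Otherwise monitor and flag the session. The choice of access stays with the treating team; the study decides only how the session is handled.
5. Add to section 9.5 a summary of the Relative Index change with and without sessions that have left-sided access.

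Cost: one reworded criterion, one CRF line per session and one extra summary. Possibly a few subjects or sessions are lost at a single center, which matters somewhat because 15 complete sets must come from at most 20 subjects, each within 30 days. Flagging sessions rather than discarding them limits that loss.

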4.4 SUBJECT WITHDRAW / EARLY TERMINATION

Subjects who withdraw from the study before using the CM-1500 device will be replaced. The reason the subject withdrew from the study may be recorded; subjects are not required to provide a reason. Subject withdrawal / early termination criteria may include but are not limited to:

- W.1 Subject requests to be withdrawn from the study or withdraws consent.
- W.2 Subject refuses or is unable to comply with required study procedures.
- W.3 An Adverse Event ("AE") makes the continuation of the subject impossible or inadvisable
- W.4 The Investigator determines it is in the subject's best interest to discontinue from the study.

5 STUDY PROCEDURES

Figure 1: Study Procedure Overview

ENROLLMENT

- Consent
- Inclusion/ exclusion criteria
- Demographics and medical history

STUDY PROCEDURE X3

- Prepare the device and subject [Subject ID ##-XX]
- Start monitoring session [wait 5+ minutes]
 - start hemodialysis procedure
- _____
- Continue monitoring post-procedure [10+ minutes] then STOP session
- Document adverse events and protocol devations
- Disconnect the subject and discard electrodes
- Repeat CM-1500 monitoring next 2 subsequent hemodialysis sessions (3 total)
- Subject participation is complete

CONFIDENTIAL Page 11 of 24

SPONSOR: ZMS

PROTOCOL: ZMS-1500-2021-Dialysis

5.1 ENROLLMENT

A subject will be considered enrolled in the study after provided written informed consent.

5.1.1 INFORMED CONSENT

The Investigator or qualified designated study personnel will complete the Informed Consent process before any study procedures may occur. The subject will be provided an IRB-approved version of the Informed Consent Form (ICF). The subject will have an ample amount of time to read the ICF and ask questions before providing written consent. The subject will receive a signed copy of the ICF. The Investigator or qualified designated study personnel will record that consent was obtained prior to performing study procedures.

5.2 BASELINE DATA

Baseline data will include collecting age, biological sex, smoking history, limited medication information, and high-level medical history.

5.3 STUDY PROCEDURE

The study procedure will consist of connecting the CM-1500 to the study subject on their left arm/wrist and starting a monitoring session at least 5 minutes prior to starting the scheduled hemodialysis procedure, wearing the monitor during the hemodialysis session, and continuing to wear the monitor for 10 minutes after the procedure is complete. The Investigator's standard post-treatment hemodialysis record will be collected containing the prescription information, machine set-up, vitals, pre- and post-treatment data collection and assessment, medications administered, and intradialytics.

5.3.1 PREPARING DEVICE FOR OPERATION

The Investigator or qualified designated study personnel will prepare the device for use by referencing the Instructions for Use (IFU) manual following the study-specific steps outlined below.

- S1. Complete the Unpacking, Inspection, and Accountability procedures and associated forms (refer to IFU for the full procedure).
- S2. Ensure the device is in a secure and stable location (refer to IFU for full procedure).
- S3. Connect the power supply cord to the display monitor and to an electrical outlet. The light will illuminate on the power adapter when it is connected to power.
- S4. Connect the CM-1500 wrist cuff trunk cable to the display monitor. The cable should double-click into the correct insertion position.
- S5. Connect the CM-1500 wrist cuff to the trunk cable. The cable should double-click into the correct insertion position.
- S6. Power on the device by pressing the external "ON/OFF" button located on the right side of the display monitor.
- S7. Press the "SETUP" button and select the desired user preferences, subject information (subject number), data storage mode, and device information. Press "SAVE" after all desired setup options are selected—the device will return to the Monitoring Screen.

CONFIDENTIAL Page 12 of 24

SPONSOR: ZMS

PROTOCOL: ZMS-1500-2021-Dialysis

- a. Select male/female
- Ensure the date/time of the CM-1500 aligns with the times that will be recorded in the
 post-treatment hemodialysis record from the hemodialysis machine and clinician
 watches
- c. Enter the subject ID as subject number (01-20) followed by AA, BB, or CC corresponding to session 1 (AA), 2 (BB), or 3 (CC). For example, the first subject, first session subject ID will be 01-AA and the next session will be 01-BB.
- S8. Insert a USB external storage drive (refer to "Data Storage Mode" in the IFU). The USB external storage drive should be labeled externally with the device serial number. The USB indicator icon should appear on the Monitoring Screen, signaling that the USB storage drive is connected and recognized.

